10.1.3. Adverse event reporting period

The investigator must start reporting non-serious AEs starting with the subject’s first study medication treatment continuing until Visit 6. Non-serious adverse events that occur between the time the subject was consent and the first application of study medication will be reported as medical history.

Reporting for SAEs begins after the subject signs the informed consent and continues until Visit 6 (regardless of relationship to study medication). If a subject experiences a SAE after Visit 6 that is deemed to be related to study medication, the investigator must report this to the Sponsor using the study specific SAE report form.

10.1.4. Severity

The investigator must define the severity of each AE using the following definitions as a guideline. The investigator will consider the range of the possible severity of the event and identify the severity that is the most appropriate according her/his medical judgment.

Mild – Awareness of signs or symptom, but easily tolerated

Moderate – Discomfort, enough to cause interference with usual activity

Severe – Incapacitating with inability to perform usual activity.

10.1.5. Relationship to study medication

The investigator will determine if there is a reasonable causal relationship between the study medication and an AE or not. The investigator will use her/his best medical judgment and consider all relevant factors (*e.g.*, temporal relationship, location of the event, the subject's relevant medical history, concomitant therapies and concurrent conditions) to determine the relationship of the AE to the study medication. The investigator will define the relationship of an AE to the study medication by selecting one of the following categories:

Related – There is a reasonable possibility that there is a causal relationship between the study medication and the AE.

Not Related – There is not a reasonable possibility that there is a causal relationship between the study medication and the AE.

The term “reasonable causal relationship” means there are facts or arguments to suggest a causal relationship (International Conference on Harmonization (ICH) E2A).

10.2. Reporting Procedures

10.2.1. Procedures for reporting adverse events

At each post enrollment visit, the investigator or designee will question the subject to elicit AEs using a non-directive question such as “Has there been any change in your health since the previous study visit?”

The investigator or designee will monitor the subject for at least 20 minutes after the Treatment Completion Time at Visit 2 and at Visit 4 to elicit AEs in a similar manner.

If appropriate, based on the subject's response to non-directed questioning regarding AEs, the investigator or designee will follow-up with directed questions and appropriate evaluations.

Any AE noted during the reporting period must be reported in the source documents and on the appropriate AE CRF.

AEs that are defined as “Not Related” to the study medications will be followed until they are resolved or until the subject’s last study visit. AEs that are defined as “Related” to the study medications will be followed until they are resolved or, if not resolved after the subject’s last study visit, until in the opinion of the investigator, the AE reaches a clinically stable outcome with or without sequelae.

10.2.2. Procedure for reporting a serious adverse event

Upon becoming aware of a SAE occurring during the AE reporting period, whether or not related to the study medications, the investigator must:

1. Take the appropriate medical action to ensure the subject’s safety
2. Immediately inform the Drug Safety Monitor of the SAE by telephone:

[name]
Aclaris Therapeutics, Inc.
[name]
[name]
[contact]
Serious Adverse Event [contact]
Email: [contact]

3. Within 24-hours complete, as fully as possible, an AE CRF and an SAE form; fax or e-mail the forms and any other relevant information (*e.g.*, concomitant medication CRF, medical history CRF, laboratory test results) to the Drug Safety Monitor.
4. Monitor and document the progress of the SAE until it resolves or, if not resolved after the subject’s last study visit, until in the opinion of the investigator the AE reaches a clinically stable outcome with or without sequelae AND the investigator and Drug Safety Monitor agree that the SAE is satisfactorily resolved.
5. Inform the Drug Safety Monitor of SAE updates by telephone followed by an SAE form update sent by fax or by e-mail.
6. Comply with the appropriate regulatory requirements and Aclaris Therapeutics, Inc. instructions regarding reporting of the SAE to the responsible Institutional Review Board (IRB) or Ethics Committee (EC).

10.2.3. Withdrawal Due to an Adverse Event

Any patient who experiences an adverse event may be withdrawn from study drug at any time at the discretion of the investigator. If a patient is withdrawn wholly or in part because of an adverse event, both the adverse events page and termination page of the CRF will be completed at that time. The patient will be monitored until the event has resolved or stabilized, until a determination of a cause unrelated to the study drug or study procedure is made, or until the patient is referred to the care of a local health care

professional. The investigator must inform the medical monitor as soon as possible of all patients who are being considered for withdrawal due to adverse events. Additional reports must be provided when requested.

11. PREGNANCY

WOCBP include any female who has experienced menarche and who has not undergone successful surgical sterilization (*e.g.*, hysterectomy, hysteroscopy, bilateral tubal ligation, bilateral oophorectomy or bilateral minilaparotomy) or is not postmenopausal. Postmenopausal is defined as ≥ 12 months with no menses without an alternative medical cause. Women who are WOCBP and are using an active method of birth control, are practicing abstinence or where the partner is sterile (*e.g.*, vasectomy), should be considered to be WOCBP.

All WOCBP must use an active method of birth control during the course of the study, in a manner such that risk of failure is minimized. Abstinence or having a sterile partner is not an active method of birth control.

Prior to trial enrollment, WOCBP must be advised of the importance of avoiding pregnancy during trial participation and the potential risk factors for a pregnancy. The subject must sign an informed consent form documenting this discussion. During the trial, all WOCBP will be instructed to contact the investigator immediately if they suspect they might be pregnant (*e.g.*, missed or late menstrual period).

If a subject or investigator suspects that the subject may be pregnant prior to study medication administration, the study medication must be withheld until the results of a pregnancy test are available. If pregnancy is confirmed, the subject must not receive study medication and must be discharged from the study.

If, following study medication administration, it is determined that the subject may have been or was pregnant at the time of study medication exposure (including at least 2 days after study medication administration) the investigator must immediately notify the Medical Monitor and record the event on a pregnancy surveillance form. While not an AE or SAE, the investigator must report every pregnancy using a pregnancy surveillance form and follow the reporting procedures described for SAE reporting (Section 10).

Protocol-required procedures for trial discontinuation and follow-up must be performed on the subject unless contraindicated by pregnancy (*e.g.*, x-ray studies). Other appropriate pregnancy follow-up procedures should be considered if indicated. In addition, the investigator must report to the Medical Monitor on the pregnancy surveillance form, follow-up information regarding the course of the pregnancy, including perinatal and neonatal outcome. Infants should be followed for a minimum of six weeks.

12. STATISTICAL CONSIDERATIONS

12.1. Sample Size and Power Considerations

The results of this first DPN study are intended to provide the data required for sample size estimation for future studies.

12.2. Statistical Analysis of Efficacy Data

Efficacy summaries and analyses (where appropriate) will be based on the per protocol (PP) population of all treated subjects completing all treatment visits and Visit 8 with no major protocol violations. In addition, efficacy summaries may be presented for the intent to treat (ITT) population of all treated subjects with at least one post-baseline visit, using last observation carried forward (LOCF) to impute missing data. Efficacy endpoints will include summary statistics (frequency distributions, proportions, means, medians and standard deviations, as appropriate) by visit for the following parameters: Physician's DPN Lesion Assessment scale results per treated lesion, subject responders defined by Physician's DPN Lesion Assessment scale outcome, and changes from baseline treated lesion diameter.

Comparative inferential analyses will be conducted for data collected from subjects in Cohort 2. The primary efficacy comparisons between the two Cohort 2 treatment groups will be made on the per-subject mean change across all treated lesions in Physician's DPN Lesion Assessment scale from baseline to the final visit using an ANCOVA model. A similar secondary analysis will be performed on the pre-subject mean percent of treated lesions that are clear (PLA=0), and a similar analysis based on clear or near-clear lesions (PLA < 2). Another secondary analysis will be performed on subject responders with all treated lesion PLA scores = 0, as well as a similar analysis on subject responders with all treated lesion PLA scores < 2. An analysis of change from baseline lesion diameter will be conducted using the same methodology as the primary efficacy analysis. All analyses will be conducted at each post-baseline visit where possible. Summaries will also be presented by subject Fitzpatrick Skin Type.

12.3. Exploratory Analysis

Exploratory efficacy endpoints will include summary statistics (frequency distributions, proportions, means, medians and standard deviations, as appropriate) by visit for the following parameters: Subject Self-Assessment scale results per treated lesion, and subject responders defined by Subject Self-Assessment scale outcome. Analyses similar to the secondary analyses described above will be conducted on the Subject Self-Assessment scale results. Summaries will also be presented by subject Fitzpatrick Skin Type. Summaries will be based on the PP population

12.4. Statistical Analysis of Safety Data

Safety analyses will include descriptive statistics calculated on the safety parameters using the ITT population. The proportion of subjects with treatment-emergent adverse events will be tabulated and presented by study treatment group and Medical Dictionary for Regulatory Activities (MedDRA) System Organ Class. Vital signs, LSR scores and clinically relevant abnormal laboratory results will also be tabulated and presented.

Data from all treated subjects will be presented and summarized. Safety summaries by study treatment group will include listings by study medication of adverse events incidences within each MedDRA System Organ Class, and changes from pre-treatment values in vital signs. Adverse event summaries will be presented showing the proportion of subjects experiencing adverse events, both overall and by MedDRA System Organ Class.

13. QUALITY CONTROL AND QUALITY ASSURANCE

13.1. Protocol Amendments

No changes from the final approved (signed) protocol will be initiated without the prior written approval or favorable opinion of a written amendment by the IEC/IRB, except when necessary to eliminate immediate safety concerns to the patients or when the change involves only logistics or administration. The principal investigator and the sponsor will sign the protocol amendment.

13.2. Protocol Deviations, Violations and Exceptions

A **protocol deviation** is non-adherence to protocol-specific study procedures or schedules that does not involve inclusion/exclusion criteria, primary objective variable criteria, and/or GCP guidelines. Deviations are considered minor and do not impact the study. Deviations include study procedures that occurred outside the treatment windows (except for treatment application days), use of prohibited medications,

A **protocol violation** is defined as any divergence from the protocol-specific inclusion/exclusion criteria, use of any prohibited medications to treat an identified DPN target lesion or a divergence from GCP guidelines. Protocol violations will be identified and recorded, by study center personnel, on the CRF.

As a matter of policy, sponsor/CRO will not grant **exceptions** to protocol-specific entry criteria to allow patients to enter a study. If under extraordinary circumstances such action is considered ethically, medically, and scientifically justified for a particular patient, prior approval from sponsor/CRO and the responsible IRB/IEC, in accordance with the Sponsor/CROs Standard Operating Procedure (SOP), is required before the patient will be allowed to enter the study. If investigative center personnel learn that a patient who did not meet protocol eligibility criteria was entered in a study (a protocol violation), they must immediately inform sponsor/CRO. Such patients will be discontinued from the study, except in a rare instance following review and written approval by sponsor/CRO and the responsible IRB/IEC, according to the applicable SOP

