1. SYNOPSIS

Protocol Number: A-101-DPN-201 Synopsis	
Protocol Title:	A Phase 2 Open Label Study of A-101 Topical Solution in Subjects with Dermatitis Papulosa Nigra
Protocol Number:	A-101-201-DPN
Sponsor	Aclaris
Phase of Development	Phase 2
Study Drug Description:	

A-101 Solution 40% is hydrogen peroxide that will be supplied in a glass ampule with an applicator to be applied to a dermatitis papulosa nigra (DPN) lesion on subjects with a Fitzpatrick Skin Type of 5 or 6.
 
The study drug, A-101 Solution 40% is a colorless solution that must be stored at room temperature (20-25° C or 68 -77 ° F), protected from light.
	
Study Objectives:	

The main objective of this study is to evaluate the safety and efficacy of hydrogen peroxide, A-101 Solution 40% for the treatment of DPN lesions on subjects with a Fitzpatrick Skin Type of 5 or 6.
	
Study Design:	

This is a phase 2 open label study to evaluate the safety of A-101 40% Solution in subjects with DPN. Subjects will be required to have up to four DPN lesions located on the subject's face or neck.
 
The first cohort of the study will enroll a total of 12 subjects (6 subjects with a Fitzpatrick Skin Type of 5 and 6 subjects with a Fitzpatrick Skin Type of 6) will be enrolled to the study.
 
The second cohort of the study a total of 24 subjects will be a randomized to a two-arm cohort. Subjects will be randomized to one of the following 2 treatment arms:
 
• A-101 40% without medically abrading the identified DPN prior to treatment• A-101 40% with the identified DPN lesions medically abraded prior to treatment 
All enrolled/randomized subjects will receive at least one application of A-101 40% solution on up to four target DPN lesions on the subject's face or neck. Subjects in cohort 1 may receive a second application of A-101 40% Solution if the lesions meet the criteria for retreatment at Visit 4 (Day 22). Subjects in cohort 2 may receive up to 3 treatment applications if the lesions meet the criteria for retreatment at Visit 3 (Day 15) and Visit 5 (Day 29). All subjects will be followed on study protocol until Visit 8 (Day 106).
 
Safety will be evaluated based on clinical laboratory studies (hematology and clinical chemistry), vital signs, urine pregnancy tests, assessment of local skin reactions (LSRs), assessment of adverse events (AEs), and concomitant medication review.
	

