5.3. Removal of Patients from Study Therapy

A subject may be removed from the study therapy for a variety of reasons, including:

- Unacceptable adverse event

- Subject unwilling or refusal to continue with the protocol defined study visits and/or consent withdrawal for study participation
- Change in compliance with an inclusion/exclusion criteria
- Pregnancy
- General or specific changes in the subject's condition that render the subject unacceptable for further treatment in this study in the judgement of the investigator.

If a subject is to be withdrawn from the study, the Aclaris Therapeutics, Inc. study monitor or designee must be informed of the decision to remove the subject from the study.

The study may be discontinued at the discretion of Aclaris Therapeutics, Inc. Some examples of reasons for discontinuation are the occurrence of the following:

- Increased frequency, severity or duration of known AEs
- Medical, regulatory or ethical reasons affecting the continued performance of the study
- Difficulties in the recruitment of subjects.

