5.4. Withdrawal Procedures

If a subject withdraws from the study prior to Visit 8, the reason for and the date of withdrawal from the study must be recorded on the eCRF. If the reason for withdrawal is an adverse event or a clinically significant abnormal laboratory test result, monitoring of the subject will continue until the event has resolved or stabilized, until the patient is referred to the care of a local health care professional, or until a determination of a cause unrelated to the study drug or study procedure is made.

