5.5. Subject Replacement

If a subject is enrolled to the study but does not receive a dose of study drug, then the subject will be replaced.

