8.1.3. Lesion Dimensions

At Visit 1 and at Visit 2 prior to enrollment the Investigator will be required to measure the diameter and thickness of each Target DPN Lesion. For subjects enrolled to cohort 1 the investigator will measure the diameter of each Target DPN Lesion using the ruler at Visit 4 (prior to retreatment, if applicable), Visit 6, Visit 7 and Visit 8. For subjects randomized to cohort 2, the investigator will measure the diameter of each Target DPN Lesion t Visit 3 (prior to retreatment if applicable), Visit 4, Visit 5 (prior to retreatment if applicable) Visit 6, Visit 7 and Visit 8.

At Visit 1 for the subject to be enrolled and at Visit 2 for the subject to be enrolled each Target DPN Lesion must have:

- A diameter that is between 2 mm and less than 5 mm.
- A height or thickness that is ≤ 2 mm.

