9.1. Local Skin Reactions (LSR)

The LSR assessment is the investigator's assessment of the signs and the subject's assessment of the symptoms associated with irritation at each Target DPN Lesion site, which includes the Target DPN Lesion and the area immediately surrounding the Target DPN Lesion.

Local Skin Reactions:

- Signs (assessed by the investigator):
 - Erythema
 - Edema
 - Scaling/dryness
 - Vesicles/bullae
 - Crusting
 - Erosion
 - Ulceration
 - Post-inflammatory hyper-pigmentation
 - Post-inflammatory hypo-pigmentation (does not include the superficial transient skin blanching/whitening related to the action of the study medications)
 - Atrophy
 - Scarring.
- Symptoms (assessed by the subject):
 - Stinging/burning
 - Pruritus (itch).

At Visits 2-8, the investigator and the subject will evaluate the LSR signs and the LSR symptoms at each Target DPN Lesion site respectively.

The investigator will assess the LSR signs as follows:

- Visits 2 and 4 (cohort 1) and Visits 2, 3 and 5 (cohort 2):
 - For each Target DPN Lesion site report the severity for all signs prior to any study medication treatment

- For every treated Target DPN Lesion site, 20 (\pm 4) minutes after the Treatment Completion Time, report the severity for the following signs:
 - Erythema
 - Edema
 - Scaling/dryness
 - Vesicles/bullae
- Visits 3 and 5-8 (cohort 1) and Visits 4 and 6-8 (cohort 2):
 - For each Target DPN Lesion site, report the severity for all signs.

The subject will assess the LSR symptoms as follows:

- Visits 2 and 4 (cohort 1) and Visits 2, Visit 3 and Visit 5 (cohort 2):
 - For each Target DPN Lesion site report the average of the severity over the previous 24 hours for all symptoms prior to any study medication treatment
 - For every treated Target DPN Lesion site, 10 (\pm 4) minutes after the Treatment Completion Time, report the average of the severity of the LSR for all symptoms since completion of the study medication treatment.
- Visits 3 and 5-8 (cohort 1) and Visits 4 and 6-8 (cohort 2):
 - For each Target DPN Lesion site, report the average of the severity over the previous 24 hours for all symptoms.

Both the subject and the study staff member will initial and date the source document to indicate the subject performed the LSR for symptoms as instructed. The staff member must not influence the subject's assessment.

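### Section 13.2 takes subjects found ineligible out of the study even after dosing, so their remaining scheduled skin and lesion readings are not collected

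*Protocol*

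**What the plan says.** Protocol section 13.2 deals with subjects who were entered although they did not meet the eligibility criteria: "Such patients will be discontinued from the study, except in a rare instance". The exception requires the sponsor/CRO and the IRB/IEC to review the case and approve it in writing, under an SOP that is not among the documents. The section does not separate dosed from undosed subjects, or stopping study medication from stopping observation.

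Other sections bear on what follows:

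- **Section 5.3** lists "Change in compliance with an inclusion/exclusion criteria" among the reasons why a subject may be removed from study *therapy*.
- **Section 5.4** requires the reason and date of any withdrawal before Visit 8. It adds: "If the reason for withdrawal is an adverse event or a clinically significant abnormal laboratory test result, monitoring of the subject will continue". No other reason for withdrawal triggers further observation.
- **Section 5.5** covers undosed subjects only: "If a subject is enrolled to the study but does not receive a dose of study drug, then the subject will be replaced".
- **Section 9.1** sets the skin schedule: "At Visits 2-8, the investigator and the subject will evaluate the LSR signs and the LSR symptoms at each Target DPN Lesion site respectively". The signs include scarring, atrophy and post-inflammatory hyper- and hypopigmentation.
- **Section 8.1.3** has the cohort 2 diameter measured at Visit 3, Visit 4, "Visit 5 (prior to retreatment if applicable) Visit 6, Visit 7 and Visit 8". PLA (section 8.1.2) also runs to Visit 8.
- **Section 6** (both cohort schedules) contains no early-termination visit.
- **SAP section 3.2.1** defines the Safety set as every treated subject, and ITT as treated subjects with a post-baseline visit. PP requires all treatment visits, Visit 8 and no major violation.

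**The concern.** Once a subject has been exposed, a later finding of ineligibility does not undo the exposure, and what happens to the skin afterwards is still safety information. Safety is part of the primary objective. Scarring and pigment change can appear late, which is a reason to score LSR through Visit 8. As written, section 13.2 ends that observation for an administrative reason, although the remaining visits are already scheduled and the subject may be willing to attend.

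Two things are at stake. First, safety follow-up of exposed subjects becomes incomplete. The SAP (section 3.7.3) closes the treatment-emergent AE window 30 days after the last treatment. After that, the by-visit LSR tables of SAP section 3.7.2 are the main planned summary of late scarring or pigment change. Second, a Visit 8 PLA that could have been obtained is imputed in the ITT repeat of the primary analysis.

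**Working it through.** The plan has no figure of its own to reproduce: section 12.1 gives no sample-size calculation. The check is a reading of the rules followed by simple arithmetic for scale.

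**1. Path of a dosed subject found ineligible before Visit 8**

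- Section 13.2: leaves the study, unless the rare exception is approved.
- Section 5.4: reason and date are recorded. An eligibility withdrawal does not trigger continued monitoring.
- Section 6: no early-termination assessment exists.
- Section 5.5: not replaced, because a dose was given.
- Section 10.2.1: an AE already reported and judged related is still followed until resolved or stable. This does not supply the scheduled LSR, PLA or diameter readings, and does not detect a later change.

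**2. What is lost in one example (ineligibility found on Day 22, after that day's assessments)**

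- Follow-up lost: 106 − 22 = 84 days, out of 106 − 1 = 105. 84/105 = 80%.
- LSR visits kept: Visits 2, 3 and 4. LSR visits lost: Visits 5, 6, 7 and 8.
- PLA and diameter lost: Visits 6, 7 and 8 in cohort 1; Visits 5, 6, 7 and 8 in cohort 2.
- If the only dose was on Day 1, the treatment-emergent AE window ends on Day 1 + 30 = Day 31.

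**3. Share of late data lost per case**

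Cohort 2 has 24 subjects randomized 1:2 (Protocol section 7.2), so 24 × 1/3 = 8 in Arm A and 24 × 2/3 = 16 in Arm B. Cohort 1 has 12, and the total is 36. Share = 1/n.

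| Group | n | One case |
|---|---|---|
| Arm A | 8 | 12.5% |
| Arm B | 16 | 6.3% |
| Cohort 1 | 12 | 8.3% |
| All | 36 | 2.8% |

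**4. Effect on what can be said if no scarring is seen**

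One-sided 95% upper bound with zero events = 1 − 0.05^(1/n).

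| Group | None lost | One lost | Two lost |
|---|---|---|---|
| Arm A | 31.2% (n=8) | 34.8% (n=7) | 39.3% (n=6) |
| Arm B | 17.1% (n=16) | 18.1% (n=15) | 19.3% (n=14) |
| All | 8.0% (n=36) | 8.2% (n=35) | 8.4% (n=34) |

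The numbers lost (0, 1 or 2) are assumptions, since the documents give no frequency.

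**5. Effect by analysis set**

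- *Safety*: the subject remains and earlier readings count, including in the maximum-severity table across visits. Later visits are missing.
- *ITT*: the subject remains if there was a post-baseline visit. The later PLA values in the primary-endpoint repeat are carried forward (SAP section 3.6.1).
- *PP*: the subject is out, because Visit 8 is missing.

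**The case against.** Much of the case on the other side stands, and it limits the point.

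- **No true contradiction.** The Synopsis and SAP section 2 say that all subjects are followed to Visit 8, and a reader might infer that section 13.2 contradicts them. Those are general statements of design, and sections 5.3 and 5.4 openly provide for removal and withdrawal. A specific withdrawal rule beside a general plan is not a contradiction. The gap in follow-up does not depend on there being one.
- **Not all scarring and pigmentation data are lost.** A reader might also infer that these signs are scored only late, at Visits 6 to 8. Section 9.1 has all signs scored at Visits 2 to 8; only the 20-minute post-treatment reading is restricted to four signs. What goes missing is the later readings.
- **Bias is not shown.** It is tempting to say that scarring and pigmentation rates are biased downward. That is plausible for exclusions 3 and 4 (hypertrophic scar or keloid; prolonged hyperpigmentation), which rest on history that may come to light late. Most of the ten inclusion and ten exclusion criteria do not concern such risk, and for those the direction is unknown.
- **Safeguards exist.** Eligibility is rechecked at Visit 2 before dosing, undosed subjects are replaced, and an approved exception is possible. These reduce the number of cases but do not provide follow-up for one that occurs. The SOP cited in 13.2 may address follow-up, but the protocol does not say so.
- **The effect on efficacy is small.** Efficacy analyses use PP, and LOCF affects only the ITT repeat of the primary endpoint.

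What survives is that the text, followed as written, gives up obtainable observations on exposed subjects. Section 7.6 already separates treatment from participation: refusing retreatment at Visit 4 does not by itself remove a subject from the study.

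**Conclusion.** The point holds as a gap in follow-up. Sections 13.2 and 5.4 together end scheduled observation of a dosed subject found ineligible before Visit 8, and no early-termination assessment fills the gap. The result is incomplete safety follow-up, plus an avoidable imputation in the ITT repeat of the primary analysis.

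The size is modest. Each case costs one subject's later readings, which matters most in Arm A because that arm has only 8 subjects. Across all 36 the effect on precision is slight. This rests on the planned 1:2 split being achieved exactly, and on ineligibility coming to light after dosing and before Visit 8 without an approved exception. How often that happens is not stated and may be never.

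**What to change.** In sections 13.2 and 5.4, state that a subject who has received study medication and is later found ineligible continues the scheduled LSR, AE, PLA, diameter and photography assessments, each on its existing schedule, through Visit 8 unless consent is withdrawn.

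State also that such subjects are excluded only from PP. This needs saying because a subject who now completes Visit 8 would otherwise be excluded only if the violation counts as major, a term the documents do not define. Safety membership already follows from SAP section 3.2.1, as does ITT membership once there is a post-baseline visit, so neither definition needs changing.

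Whether such a subject receives further applications is a separate matter. Section 13.2 (removal from the study) and section 5.3 (possible removal from therapy) must be reconciled by the sponsor on that; the change proposed here concerns observation only.

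The cost is a protocol amendment, which section 13.1 makes subject to prior IRB/IEC approval, and a few visits for subjects who will not be in PP. Those visits and procedures are already in the schedule.
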